7.2.2 Immune system disorders

Immune system disorders judged to be driven by autoimmunity by the investigator and grade 3 or above for suspected CRS, if related to adjuvanted or non-adjuvanted ES2B-C001 as judged by the treating physician should lead to pause in trial treatment and follow-up and following action should be taken by the investigator:

- Initiate appropriate symptomatic treatment.
- Fill in designated eCRF page + SAE page, if applicable.
- Notify sponsors, and CROs medical monitor immediately and plan for further evaluation.
- Evaluate with sponsor, and CROs medical monitor ~2 weeks post event for continuation in trial on treatment, or early treatment discontinuation, to the farthest extent possible continued participation for safety follow up should be pursued.

7.3 Patient Withdrawal from the Trial

- A patient may withdraw from the trial at any time at the patient's own request for any reason (or without providing any reason).
- A patient may be withdrawn at any time at the discretion of the investigator for safety or compliance reasons.

Clinical Study: ES2B-C001-S01 EU CT No.: 2024-516333-12-00

- At the time of discontinuing from the trial, if possible, an early termination visit should be conducted, as shown in the SoA (Section 1.3).
- The patient will be permanently discontinued from the trial intervention and the trial at that time.
- If the patient withdraws consent for disclosure of future information, the sponsor may retain and continue to use any data collected before such a withdrawal of consent.
- If a patient withdraws from the trial, the patient may request destruction of any samples taken and not tested, and the investigator must document this in the site trial records.

7.4 Lost to Follow-up

A patient will be considered lost to follow-up if the patient repeatedly fails to return for scheduled visits and is unable to be contacted by the trial site.

The following actions must be taken if a patient fails to return to the clinic for a required trial visit:

- The site must attempt to contact the patient and reschedule the missed visit as soon as
 possible, counsel the patient on the importance of maintaining the assigned visit schedule
 and ascertain whether the patient wishes to and/or should continue in the trial.
- Before a patient is deemed lost to follow-up, the investigator or designee must make every
 effort to regain contact with the patient (where possible via 3 telephone calls, and if
 necessary, a certified letter to the patient's last known mailing address or local equivalent
 methods). These contact attempts should be documented in the patient's medical record.
- Should the patient continue to be unreachable, the patient will be considered to have withdrawn from the trial.

7.5 Criteria for Temporarily Delaying Enrollment in the Trial and Stopping Rules

Enrollment of new patients in the trial will be temporarily halted if 2 or more out of 6 patients experience DLTs in the same dosing group (as per Section 4.3.2).

In these cases, DLT level has been reached and enrollment at that dose level cannot continue if DLTs are confirmed. The DSMB will review all available, accumulated safety data and recommend further course of action and potentially identify intermediate lower doses for further testing.

The trial includes following trial stopping criterion:

- DSMB recommendation based on patients' medical data and intolerable toxicities.
- Decision from the sponsor to terminate the trial.

8 Trial Assessments and Procedures

For timing of assessments and procedures, refer to the SoA presented in Table 1 (Section 1.3).

Clinical Study: ES2B-C001-S01 EU CT No.: 2024-516333-12-00

In the event of a significant trial-continuity issue (e.g., caused by a pandemic), alternate strategies for patient visits, assessments, medication distribution and monitoring may be implemented by the sponsor or the investigator, as per international, national or local health authority/ethics requirements.

8.1 Screening/Baseline Assessments

Patients will be informed about all aspects of the study including the purpose and risks, having the possibility to clarify the questions they may have. Any study-specific assessment may only be done after the patient has signed the ICF. An eligibility screening can take place within 28 days prior to the first dose administration.

All screening evaluations must be completed and reviewed to confirm that potential patients meet all eligibility criteria. The investigator will maintain a screening log to record details of all patients screened and to confirm eligibility or record reasons for screening failure, as applicable.

8.1.1 Demography

The following demographic data will be recorded:

- Year of birth and age.
- Sex: female, male.
- Ethnicity (if allowed by local legislation).

8.1.2 Smoking status

Never, current, previous smoker and duration of smoking.

8.1.3 Medical and Surgical History

Relevant general medical and surgical history including concurrent diagnoses within the previous 12 months, or longer if considered clinically significant, must be reported.

For each condition, diagnosis, or surgical procedure, the start date and stop date will be recorded; it will also be recorded if the condition or diagnosis is ongoing.

Relevant medical history also includes diseases which are specifically listed as exclusion criteria and diseases for which specific treatments are listed as exclusion criteria.

8.1.4 History of Breast Cancer

First onset of breast cancer must be documented, along with any primary surgery, and first diagnosis of metastatic breast cancer (if this differs from first onset of breast cancer), cancer stage including TNM classification, histological grade, HER2 as well as hormone receptor status All previous neo-adjuvant and adjuvant treatment regimens must be noted (type of compounds, number of cycles, overall duration), as well as all previous lines of therapy in the metastatic setting (type of compounds, number of cycles, overall duration) (see Section 6.9.1).

Clinical Study: ES2B-C001-S01 EU CT No.: 2024-516333-12-00

A history prior of axillary lymph node dissection must be taken, and documented in the eCRF, it must also be documented if axillary lymph node dissection has not been performed. If a limited number of sentinel nodes have been removed, this must be documented.

8.1.5 Height and Weight

The patients' height (cm) and weight (kg) as well as BMI (kg/m²) will be measured or calculated, respectively, and will be recorded in the eCRF.

8.1.6 Viral Serology

Viral serology to HBsAg, HCV antibody, and/or HIV types 1 and 2 antibodies will be assessed during screening period.

8.2 Efficacy and Immunogenicity Assessments

Planned timepoints for all efficacy and/or immunogenicity assessments are provided in the SoA (Section 1.3).

Objective response rate (ORR), DCR, PFS, DFS, and OS, following RECIST 1.1 will be assessed by the investigator according to routine follow up.

8.2.1 Immunogenicity Assessments

Samples will be collected from all patients according to the SoA. Additionally, serum samples should be collected at the final visit from patients who discontinued trial intervention or were withdrawn from the trial.

Antibodies to ES2B-C001 will be evaluated in serum samples collected from all patients. Samples will be screened for antibodies binding to HER2 and the titer of confirmed positive samples will be reported.

Anti-HER2 antibodies and titers will be evaluated by enzyme-linked immunosorbent assay (ELISA) after last administration for all patients (up to Day 127 sample), or as applicable.

Isotyping of anti-HER2 Immunoglobulins in serum will be performed by ELISA or immunocapture LC/MS for determination of e.g. IgM, IgG (IgG1-4), IgD, IgE, IgA.

Other analyses may be performed to verify the stability of antibodies to HER2 and/or further characterize the immunogenicity of ES2B-C001.

The detection and characterization of antibodies to HER2 will be performed by central or special laboratory using a validated assay method by or under the supervision of the sponsor. Details regarding sample collection and processing will be provided in the Laboratory Manual.

Clinical Study: ES2B-C001-S01 EU CT No.: 2024-516333-12-00

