2.1.3 HER2 and HER2 vaccines

HER2 is a tumor-associated antigen, which is overexpressed on some tumor cells and to a lesser extent expressed on normal cells, which makes HER2 an obvious target for therapeutic cancer vaccines. Thus, HER2 is a self-protein. Most self-proteins in the body, such as HER2, are not antigenic because of established self-tolerance, a process in which self-reacting cytotoxic T-lymphocytes and autoantibody-producing B-lymphocytes are deleted or inactivated "centrally" in the thymus and "peripherally" in the spleen and lymph nodes when exposed to self-antigens in a non-danger signal context. Conversely, any self-protein, that for some reason has not been

Clinical Study: ES2B-C001-S01 EU CT No.: 2024-516333-12-00

exposed to the immune system in the thymus, may later trigger an immune response, since central self-tolerance has not been developed. This may include normal proteins that are well sequestered from the immune system, proteins that are normally produced in extremely small quantities, or proteins whose structure is modified due to mutation.

Historically, very few HER2-reactive T cell responses in healthy individuals have been identified. This finding is indicative of either a lack of prior exposure to HER2 epitopes or tolerance. The data points to the lack of prior exposure, as HER2 epitope and protein vaccines elicit T-cell and antibody immunity that remain stably elevated for at least two years after last vaccine

The definition of HER2-positive breast cancer is based on patients expected to benefit from immunotherapy (e.g. trastuzumab and pertuzumab) per the inclusion criteria used in pivotal trials. Low expressing HER2 (IHC 1+, or 2+ and no gene expression/FISH -) may be a distinct, clinically relevant breast cancer population warranting reassessment of traditional diagnostic and therapeutic paradigms (Prat et al., 2022). Up to 85% of patients have traditionally defined HER2-negative breast cancer and are ineligible for current anti-HER2 directed therapies; however, 50% of patients with HER2-negative BC have low levels of HER2 expression.

HER2-low patients were extensively studied in multiple HER2 vaccine trials over the last two decades, summarized in Table 2.

Table 2: Overview of Vaccine Trials in HER2-low Patients.

First author/year of publication	Vaccine	Population	Safety	Efficacy

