2.4 Overall Benefit-Risk Conclusion

In conclusion, this trial aims to evaluate the safety profile of the novel HER2-directed vaccine ES2B-C001 with and without adjuvant. The risks for the patients participating in the trial are considered low and it is expected that the polyclonal anti HER2 antibody response will have anticancer effects beneficial to patients participating in the trial. The overall risk-benefit-ratio of participating in this trial is judged to be favorable in patients

3 Trial Objectives and Endpoints

Table 3: Description of the objectives and endpoints of this clinical study.

Objectives	Endpoints			
Primary				
To determine the safety, tolerability, maximum tolerated dose (MTD) for ES2B-C001 alone or in combination with the adjuvant	 Nature and frequency of dose-limiting toxicities (DLTs). Incidence, nature and severity of AEs graded according to the National Cancer Institute (NCI) Common Terminology Criteria for Adverse Events (CTCAE) v5.0. Incidence, nature and severity of injection site reactions according to FDA Guidance on Toxicity Grading Scales in Vaccine Trials (FDA, 2007). 			

Clinical Study: ES2B-C001-S01 EU CT No.: 2024-516333-12-00

Objectives	Endpoints			
Secondary				
To investigate the immunogenicity of ES2B-C001 alone or in combination with the adjuvant	 Immunogenicity as humoral immune response: Total anti-HER2 Immunoglobulin titers in sera by enzyme-linked immunosorbent assay (ELISA). Isotyping of anti-HER2 Immunoglobulins in sera (e.g. IgM, IgG (IgG1-4), IgD, IgE, IgA), Optional and obligatory in the non-adjuvanted and adjuvanted treatment group, respectively. 			
Exploratory				
To determine the preliminary antitumor activity of ES2B-C001 alone or in combination with the adjuvant observed	 Percentage of patients with measurable disease at baseline achieving Complete Remission (CR) or Partial Response (PR) according to RECIST 1.1 as assessed by the investigator during routine follow up. Percentage of patients with Disease Control Rate (DCR) according to RECIST 1.1 as assessed by the investigator during routine follow up. Progression free survival (PFS) in patients with Stable Disease (SD), or PR, at the time of first dosing of ES2B-C001 alone or in combination with the adjuvant according to RECIST 1.1. Disease-free survival (DFS) in patients with CR at the time of first dosing of ES2B-C001 alone or in combination with the adjuvant according to RECIST 1.1. Overall survival (OS) 			

4 Trial Design

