9.3.2 Secondary endpoint analysis

All immunogenicity variables will be analyzed descriptively following general rules defined at the beginning of this section. In addition to the standard set of descriptive statistics, geometric mean will be reported by study visit for each population separately. For each visit after first study drug administration, the change from baseline will be analyzed descriptively.

Secondary endpoint analysis will be done on Immunogenicity Set.

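### Section 8.2.1 reports titres only for confirmed positive samples, which does not fit the all-patient Immunogenicity Set or the geometric means and changes from baseline planned in 9.3.2

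*Protocol*

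**What the plan says.** Section 8.2.1 sets out a screen-and-confirm scheme in which "the titer of confirmed positive samples will be reported". It names no titre or substitute value for a sample that is not confirmed positive.

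Two other sentences in 8.2.1 point to wider coverage. One is "Antibodies to ES2B-C001 will be evaluated in serum samples collected from all patients". The other, with its last word left off here, is "Anti-HER2 antibodies and titers will be evaluated by enzyme-linked immunosorbent assay (ELISA) after last administration for all patients (up to Day 127 sample), or as".

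Section 9.2 defines the Immunogenicity Set as dosed patients who have provided immunogenicity data. It has no condition on antibody status, and all immunogenicity analyses use it. Section 9.3 summarises continuous variables by the count of available values, mean, SD, median, minimum and maximum, by dose level. Section 9.3.2 applies those rules to every immunogenicity variable and adds that the "geometric mean will be reported by study visit for each population separately". It continues: "For each visit after first study drug administration, the change from baseline will be analyzed descriptively".

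Section 9 leaves technical detail to a SAP, to be final before database lock.

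**The concern.** The reporting rule and the summaries do not match. A patient who does not respond is in the analysis set but, under the literal rule, supplies no titre. If the summary then runs over the values available, the geometric mean describes responders while its label refers to the whole set. The overstatement is largest where responders are fewest, so it would flatten a dose-response. A patient negative before the first dose has no baseline number from which to compute a change.

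There is a second, lesser mismatch. The plan uses geometric means for titres but leaves the change from baseline on the general mean and SD scale, where one high responder can dominate.

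Titres may also be used before the SAP has to be final. The synopsis lets the DSMB consider antibody titres if available and names high variability of emerging immunogenicity data as a ground for expanding a cohort. Section 10.7 also has the DSMB review available immunogenicity data. A positives-only view could hide that variability: two titres of 1600 beside an unreported negative show no spread at all.

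**Working it through.** The protocol states no titre, cut-off, positivity rate or geometric mean, so there is no figure to reproduce. The check asks how much it matters whether negatives are kept.

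**Inputs.** Cohort sizes of 3, 6 and 9 come from Section 4.1. Assumed, not from the protocol: every positive titre is T = 1600, and a negative, when kept, is given c = 25, 50 or 100.

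**Formula.** With k negatives among n patients, the positives-only geometric mean is T. The all-patient geometric mean is (T^(n−k) × c^k)^(1/n). The inflation from dropping negatives is the ratio of the two, (T/c)^(k/n).

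For one negative in three at c = 25: (1600 × 1600 × 25)^(1/3) = 400, and 1600/400 = 4.

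| n | Negatives | Positives only | All patients, c = 25 / 50 / 100 | Inflation, c = 25 / 50 / 100 |
|---|---|---|---|---|
| 3 | 1 | 1600 | 400 / 504 / 635 | 4.00 / 3.17 / 2.52 |
| 6 | 1 | 1600 | 800 / 898 / 1008 | 2.00 / 1.78 / 1.59 |
| 9 | 1 | 1600 | 1008 / 1089 / 1176 | 1.59 / 1.47 / 1.36 |
| 3 | 2 | 1600 | 100 / 159 / 252 | 16.00 / 10.08 / 6.35 |

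**How often it could arise.** If each patient is positive with assumed probability p, the chance of at least one negative is 1 − p^n. At p = 0.8 this is 49% for n = 3, 74% for n = 6 and 87% for n = 9. For n = 3 it runs from 88% at p = 0.5 to 27% at p = 0.9.

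**Change from baseline.** A patient negative at baseline who reaches 1600 has no defined change if the baseline is blank. Once a value is assigned, the fold rise is 1600/25 = 64, 1600/50 = 32 or 1600/100 = 16. It can be computed, but it depends on the value chosen.

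**Scale.** For assumed rises of 100, 200 and 25600, the arithmetic mean is 25900/3 = 8633, the geometric mean is (100 × 200 × 25600)^(1/3) = 800, and the median is 200.

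**The case against.** A reader might infer that the plan removes non-responders from the geometric means and that change from baseline cannot be computed for baseline-negative patients. The documents do not support either as a fixed consequence. The reporting sentence sits in an assessment section and can be read as a description of laboratory output. Section 9.2 keeps negative patients, 8.2.1 also speaks of titres for all patients, and no passage excludes negatives. Once a value is assigned to them, both summaries can be computed. That value is properly a matter for the SAP or laboratory manual, and its absence here is not a finding.

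It is also tempting to say that most patients will be negative at baseline. The remark in Section 2.1.3 that "very few HER2-reactive T cell responses in healthy individuals have been identified" concerns T cells in healthy people, not serum antibody in patients with metastatic breast cancer. The eligibility criteria and visit schedule cannot be read in this copy, so baseline serostatus and baseline sampling cannot be judged.

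On impact, escalation rests mainly on DLTs (Section 4.3), nothing says the DSMB works from the 9.3.2 tables, and no hypothesis is tested (Section 9.1). The count of available values would reveal a summary based on two of three patients. The median, minimum and maximum would expose an outlying change. Nor are total titres the only secondary endpoint, since isotyping is listed too (Section 3, Table 3).

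All of this stands and limits the severity. It does not remove the mismatch. The all-patients sentence is confined to the time after the last administration, or as applicable, and gives negatives no value. The literal reporting rule still conflicts with the analysis set and with the summaries.

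**Conclusion.** The point holds as an inconsistency to be reconciled, not as proof that the planned results will be biased. Section 8.2.1 as worded yields titres for confirmed positives, while 9.2 and 9.3.2 call for summaries over a set that includes negatives. If the literal rule were followed, the geometric mean would be about 2.5- to 4-fold too high with one negative in three and about 1.4- to 1.6-fold with one in nine. Those sizes rest wholly on the assumed titres (1600 for positives, 25 to 100 for negatives). The scale of the change from baseline is a secondary weakness. Severity is minor to moderate: the endpoint is secondary and descriptive, but titres may be looked at during the trial for escalation and expansion.

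**What to change.** In Sections 8.2.1 and 9.3.2:

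- State that negative or below-cut-off samples stay in all titre summaries at a pre-specified value. The value itself may be set in the SAP or laboratory manual, provided this is done before titres are reviewed.
- Show the number and percentage of positive samples by visit and dose level beside the geometric mean.
- Report change from baseline as a geometric mean fold rise, alongside or instead of the arithmetic change.
- Align the two titre sentences in 8.2.1 so that it is clear which samples receive a titre and at which visits.

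The cost is a few sentences and routine programming. The downside is that headline titres become less favourable and depend somewhat on the assigned value. Showing the percentage positive makes that dependence visible.

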8.2.2 Tumor Imaging and Assessments of Disease

Throughout this section, the term 'scan' refers to any medical imaging data used to assess tumor burden and may include cross-sectional imaging (such as CT or MRI) medical photography, or other methods as specified in this protocol.

8.2.2.1 Initial Tumor Scans

At screening, patients require a baseline scan evaluated per RECIST 1.1. Tumor scans performed as part of routine clinical management are acceptable for screening if they are of acceptable diagnostic quality and performed within the allowed screening period, up to 28 days prior to start of ES2B-C001 administration.

Availability of CNS imaging in medical records, are required to evaluate radiographically detectable CNS metastases if applicable.

8.2.2.2 Tumor Scans During the Trial

After enrollment, tumor scans should be performed at routine follow up every 12 weeks (± 2-week window) for MBC or more frequently if clinically indicated. If a patient discontinues trial treatment, tumor scans should be performed at the time of discontinuation (± 2-week window) unless previous scans were obtained within 2 weeks of discontinuation.

8.3 Safety Assessments

Planned timepoints for all safety assessments are provided in the SoAs.

8.3.1 Assessment of the injection site

In the eCRF the injection site (shoulder, thigh, or buttocks) and side (right or left), must be documented. It must be documented that the region of choice has no clinically significant findings prior to administration of adjuvanted ES2B-C001 (see Section 6.3 for details).

8.3.2 Physical Examinations

- A complete physical examination will include, at a minimum, assessments of the cardiovascular, respiratory, gastrointestinal, and neurological systems.
- A brief physical examination will include, at a minimum, assessments of the skin, lungs, cardiovascular system, and abdomen (liver and spleen).
- Investigators should pay special attention to clinical signs related to previous serious illnesses and previous reaction to vaccines.

8.3.3 Vital Signs

• Body temperature (°C), pulse rate (bpm), respiratory rate (breaths/minute), and supine blood pressure [mmHg] will be recorded (before blood collection for laboratory tests).

Clinical Study: ES2B-C001-S01 EU CT No.: 2024-516333-12-00

- Blood pressure and pulse measurements will be assessed with a completely automated device. Manual techniques will be used only if an automated device is not available.
- Vital signs will be measured after 5 minutes rest and will include tympanic body temperature, systolic and diastolic blood pressure, and pulse and respiratory rate.

